All OER orthopedic doctors and nurses are trained and skilled in the closed reduction technique and forearm circular cast application. The closed reduction technique, done manually by three operators, and circular cast application are performed as described in Dresing et al. (2017).

Patients' enrolment

After having performed the necessary radiographic investigations and verified the presence of all inclusion criteria and the absence of exclusion criteria, complete oral and written information about the study will be given to each patient by OER nurses and physicians. A reflection period will be guaranteed to the patient during the waiting time before the control X-ray after reduction procedure.

Enrolment will be effective as soon as the patient has signed the consent form. We will then assign him/her to the intervention or control group after a telephone call to the Data Analysis Manager, as described in the following section.

Randomization, blind and control

We will generate the randomization list through the program called "Random Number Generator", available at <https://stattrek.com/statistics/random-number-generator.aspx>. The randomization will be simple with 1:1 allocation. The randomization list, known only to the Data Analysis Manager not involved in the clinical evaluation of patients, will be implemented and hidden inside a specific file protected by a password to prevent identification of the patient. We will assign the enrolled patients to group 0 or 1 according to the list by a telephone contact between Investigators and Data Analysis Manager.

The data-analyzing Researcher will not know which of the two groups will be the intervention nor the control one, to guarantee the blind. The Investigators are not allowed to collect data in a blind way due to the nature of study intervention.

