Blow (2015) suggests that the tape application needs to be proximal to the plaster cast. However, this indication is not supported by the literature. Other authors apply tape on the area that will probably form oedema (Donec, et al.,2014). Therefore, we believe that tape application on hand fingers is the most appropriate for achieving the objectives of this study.

The tape available at the Local Health Unit of Piacenza is the Leukotape K® by Essity, winner of the INTERCENTER AVEN tender for the supply of this type of medical device.

CRFs will be kept in OER until follow-up, so that any re-attendances can be noted.

Follow up

Even though tape results could be seen after 2-3 days, we choose to collect T1 variables (as previously described) at day 7 in order to avoid possible bias in the re-entry evaluation. The 7-day follow-up will be concomitant with the radiographic fracture control provided by organization procedure.

The completed CRFs will be delivered to the Researcher who will carry out the data analysis.

Statistical analysis

We will describe the general characteristics of the two groups. We will evaluate the effectiveness of randomization through the χ^2 test, for categorical variables, and the t-test, for continuous variables. Intervention group versus control group analyses will be performed by comparing the respective mean of: the T0-T1 differences of circumference of both thumb (*i*) and the other 4 fingers (*ii*), the pain NRS score at T1(*iii*), and the number of OER re-entries (*v*), by t-test for independent groups (after verifying the normality of the distributions with the Shapiro Wilk test).

All analyses will be performed on an Intention-To-Treat principles: all randomized patients will be analyzed in the arm they were allocated by randomization. Only screening failures and patients

who refuse before the treatment start would be excluded. In the event of tape detachment in the first 48 hours after T0 and/or impossibility to evaluate study endpoints, missing data will be substituted by multiple imputation.

We will perform all analyzes using 2-tailed tests and consider significant a p value <0.05. We will report all analyzes according to the international guidelines for RCTs (Boutron et al., 2017).

REFERENCES

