* Further exclusion criteria introduced following advices of Blow and Kumbrink although to date there are no absolute contraindications to the application of elastic tapes (Blow, 2015; Kumbrink et al., 2019).

Table 2: Variables of study CRF and study timepoints.

Variable name	Unit of measurement or possible categories	T0 (day1)	T1 (day7)
Subject code	N/A	X	
Gender	Male/Female	X	
Age	Years	X	
Heart disease	Presence/Absence	X	
Kidney pathologies	Presence/Absence	X	
Respiratory diseases	Presence/Absence	X	
Diabetes	Presence/Absence	X	
Hypertension	Presence/Absence	X	
Assigned group	0/1	X	
Fractured limb	Right/Left	X	
1 st finger circumference	Cm	X	X
Circumference of the remaining 4 fingers merged together	Cm	X	X
NRS	0-10	X	X
Analgesic use during the previous 4 hours	Yes/No	X	X
Accidental removal in the 48 hours after T0	Presence/Absence		X
Accidental removal	Presence/Absence		X
OER re-attendance between T0 and T1	Natural number		X

FIGURE LEGENDS

Figure 1. CONSORT flowchart modified for Randomized Trials of Nonpharmacologic Treatments (Boutron et al., 2017)

Figure 2. Tape application: a. lateral view, b. sight fly, c. dorsal view

FIGURES

[figure not shown]

Figure 1

Figure 2.

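### Baseline significance tests cannot judge the randomisation, and T1 pain is compared without using the T0 score already collected

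*Combined protocol and SAP*

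**What the plan says.** Under Statistical analysis the plan first promises a description: "We will describe the general characteristics of the two groups". It then gives the baseline tests a purpose: "We will evaluate the effectiveness of randomization through the" χ² test for categorical variables and the t-test for continuous variables. The threshold covers every analysis: "We will perform all analyzes using 2-tailed tests and consider significant a p value <0.05". The section does not list the variables to be tested and does not say what follows from a significant result.

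On allocation, the section on randomisation and blinding says "The randomization will be simple with 1:1 allocation". The list is held by a Data Analysis Manager who takes no part in clinical evaluation, and assignments are released by telephone after consent.

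On outcomes, the plan says "Intervention group versus control group analyses will be performed by comparing the respective mean of" four quantities, by independent-groups t-test. The two circumferences enter as T0–T1 differences. Pain enters as "the pain NRS score at T1" alone, although Table 2 ("Variables of study CRF and study timepoints") records NRS at both T0 and T1 and the secondary endpoint names both time points. No covariate adjustment appears anywhere in the document.

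**The concern.** There are two separate issues.

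**Baseline tests.** A test of group difference at baseline has as its null hypothesis that the groups differ only by chance. A concealed random list makes that null true by design. A significant result is then a false alarm, and a non-significant one does not show that an imbalance is harmless, because harm depends on how strongly the variable predicts the outcome. With several variables, a false alarm somewhere is common. As no response is specified, a reader of the report could take a false alarm as a defect, and the choice of whether to adjust is left until the data have been seen.

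**Pain.** T0 NRS is collected but not used in the T1 comparison. Any chance difference in T0 pain passes in part into the T1 result, and variance that T0 pain could explain remains in the error term.

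**Working it through.** **Inputs from the document.** Two-sided α = 0.05 (Statistical analysis). Effect size 0.4, power 0.80, 100 per arm needed and 110 per group enrolled (Sample size calculation). Table 2 has 12 patient variables at T0, leaving out subject code and assigned group:

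- 8 non-outcome variables: gender, age, heart disease, kidney pathologies, respiratory diseases, diabetes, hypertension, fractured limb.
- 4 outcome variables: thumb circumference, four-finger circumference, NRS, and "Analgesic use during the previous 4 hours".

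**Assumed, because the document does not give them.** The T0–T1 correlation r, equal SDs at T0 and T1, and, for the simulation below, prevalences and correlations among baseline variables.

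**The plan's own figure.** For d = 0.4, two-sided 0.05, power 0.80 and 1:1 allocation, the noncentral t distribution gives power 0.7997 at 99 per arm and 0.8036 at 100. The stated 100 per arm is reproduced.

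**Step 1: false alarms with sound randomisation.** For k independent tests, P(at least one p<0.05) = 1 − 0.95^k.

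- k = 12: 1 − 0.95^12 = 0.460
- k = 8 (non-outcome variables only): 1 − 0.95^8 = 0.337

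Comorbidities and age are likely to be correlated, so simple 1:1 randomisation of 220 patients was simulated with 8 χ² tests and 4 t-tests (4,000 runs per setting, assumed prevalences, common correlation among all 12 variables):

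| Correlation | χ² uncorrected | χ² with continuity correction |
|---|---|---|
| 0 | 0.47 | 0.37 |
| 0.2 | 0.45 | 0.37 |
| 0.3 | 0.41 | 0.35 |
| 0.5 | 0.38 | 0.31 |

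The 0.47 agrees with the exact 0.460 within simulation error: √(0.46 × 0.54 / 4000) ≈ 0.008. For all 12 variables the range is therefore about 31–46%.

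**Step 2: T0 pain imbalance that passes as non-significant.** The bound in SD units is 1.97 × √(2/n).

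- n = 100 per arm: 1.97 × √(2/100) = 0.28 SD
- n = 110 per arm: 1.97 × √(2/110) = 0.27 SD

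With equal SDs, the expected carry-over into the T1 difference is r times the imbalance.

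- r = 0.3: 0.3 × 0.27 to 0.3 × 0.28 ≈ 0.08 SD
- r = 0.6: 0.6 × 0.27 to 0.6 × 0.28 ≈ 0.16–0.17 SD

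For scale, the design effect is 0.4.

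**Step 3: precision gain for T1 NRS.** Adjusting for T0 multiplies the residual variance by 1 − r².

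- r = 0.3: 1 − 0.09 = 0.91, a 9% reduction
- r = 0.6: 1 − 0.36 = 0.64, a 36% reduction

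**Step 4: precision gain for the circumferences.** With both variances set to 1, a change score has variance 2(1 − r) and the adjusted analysis has 1 − r² = (1 − r)(1 + r). The ratio is (1 + r)/2, so the reduction is (1 − r)/2.

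- r = 0.6: (1 − 0.6)/2 = 20%
- r = 0.9: (1 − 0.9)/2 = 5%

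**The case against.** The strongest reply is that little in the trial depends on this.

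- **No decision rule.** The plan attaches no action to a significant baseline test, so the type I error of the outcome analyses is not directly inflated. This stands. The data analyst also does not know which code is the intervention, which limits directional post hoc adjustment but does not remove it.
- **The 46% is a ceiling.** It needs all 12 variables to be tested and independent. The section speaks only of general characteristics, which may exclude the four outcome measures. This stands, and it is why a range is given. A reader might infer that nearly half of sound trials would be declared failures. The document supports neither that count of tests nor such a declaration.
- **Baseline is not ignored.** A reader might infer that the tests are the plan's only protection against imbalance. That is wrong for both primary endpoints, which are T0–T1 differences. It is true only of NRS among the outcomes measured on a scale at both visits.
- **The unadjusted T1 test is valid.** A reader might infer that it is biased. Under randomisation it is unbiased on average, and its standard error already allows for chance imbalance. The shift in Step 2 is an unfavourable case at the significance boundary. T0 pain is scored before any local anaesthetic and T1 pain a week later in a cast, so the correlation could be low.
- **Baseline differences may have non-chance sources.** Investigators collect data unblinded, the timing of the T0 circumference relative to allocation is not stated, and patients who refuse before treatment starts are excluded. This is fair, and a baseline test might pick up such a problem. But the plan does not state that purpose, and a p-value cannot separate such a problem from chance.

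What remains is that the tests do not answer the question put to them, and that a collected covariate goes unused for pain.

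**Conclusion.** The point holds as a free improvement, not as an error that threatens the trial's conclusions. The baseline tests cannot assess the randomisation. With sound allocation at least one would be significant in roughly 31–46% of trials if all 12 T0 variables are tested, or 34% for the 8 non-outcome variables if independent. The lower end of that range rests on assumed prevalences, correlations and a continuity correction; the upper end rests on independence.

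For T1 NRS the cost is lost precision and exposure to chance imbalance, not bias. The 9–36% variance reduction and the 0.08–0.17 SD carry-over depend on an assumed T0–T1 correlation of 0.3–0.6, and the carry-over also on equal SDs. A reader might apply the 9–36% to the primary endpoints, but it does not transfer. For the change scores the gain is (1 − r)/2 under equal variances, 20% at r = 0.6 and 5% at r = 0.9.

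**What to change.** Make two wording changes under Statistical analysis.

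1. Replace the sentence on χ² and t-tests at baseline with a statement that T0 characteristics will be tabulated by group as mean and SD or number and percentage, without p-values.
2. Prespecify that T1 NRS will be compared between groups by a linear model with T0 NRS as covariate, and each circumference likewise with its own T0 value as covariate, whatever balance is observed. For the circumferences the T0–T1 difference can remain the response: with T0 in the model, the group estimate is the same as for T1, apart from sign.

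The planned multiple imputation should contain the same T0 values, so that it matches the analysis model.

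The cost is text only. Every covariate is already in Table 2, and no patients, visits or measurements are added. The change should be dated before the group codes are opened.

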The primary aim of our study is to evaluate whether the application of the tape with lymphatic technique to the fingers, both dorsal and volar, of wrist fractured patients treated with a forearm circular plaster cast is able to reduce the formation of hand oedema, compared to the untreated controls. Furthermore, we aim to assess the differences in pain and cast tolerability between the intervention group and the control group.

Primary endpoints

(i) difference in the circumference of the thumb between baseline (T0) and 7-days follow-up (T1), and (ii) difference in the circumference of the remaining 4 fingers merged together, between T0 and T1.

Secondary endpoints

(i) pain intensity at T0 and T1, (ii) analgesic use during the previous 4 hours at T0 and T1, and (iii) OER re-entry number for “intolerance to the plaster cast”.

Design

Our study is a randomized controlled superiority trial, with parallel design and blinded data processing, developed at OER of Local Health Unit of Piacenza.

The ID NCT04683887 identify this study on clinicaltrials.gov.

Participant characteristics

The patients' eligibility criteria to participate in our study are described in Table 1.

Sample size calculation

The sample size was calculated using the GPower 3.1 Software, setting the following parameters: effect size: 0.4, error α = 0.05, power = 0.80 and allocation ratio = 1.

The resulting sample size is 100 subjects per arm; the number of patients to be enrolled will be a total of 220 (110 per group), taking into account a 10% loss to follow up. The choice of medium effect size (0.4) was made based on feasibility and available literature (Gülenç et al., 2019; Pajero Otero et al., 2019; Tantawy et al., 2019) despite the absence of similar studies for pathology/type of intervention/primary endpoint.

Setting

Patient enrolment, execution of the fracture reduction maneuver, application of the plaster cast, application of the tape for the investigational treatment patient group, and endpoint T0 measurements will take place at the OER service of Local Health Unit of Piacenza. On day 7 the

tapes will be removed and endpoint T1 measurements will be assessed at the Orthopedics and Traumatology outpatient clinic.

Preliminary procedures and nurses' training

Before the enrolment of the first patient, all OER nurses will be trained for the tape application by a certified instructor.

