We decided not to apply any type of alternative strip to the control group. Even if positioned without lymphatic technique, the tape would maintain its elastic properties and we cannot exclude that it may still have an effect. The application of a strip with properties different from the tape on one side would still have the adhesive effect induced by the glue-skin interaction, stimulating muscle function (Blow, 2015; Frignani, 2017; Zimiglia, 2014), but on the other hand, having a different elasticity from that of the tape, could reduce the range of motion (ROM) of the fingers (Frignani, 2017) and potentially could increase the risk of developing oedema in the control group.

Outcome evaluation details

OER nurses will evaluate the extent of oedema in the fracture-homolateral hand by measuring the circumference at the base of the 1st phalanx of the 1st finger and at the base of the 1st phalanx of the remaining 4 fingers merged together both at T0 and T1. The number of re-entries in OER between T0 and T1 will be registered. Furthermore, we will measure the intensity of pain with the Numerical Rating Scale (NRS) (Artioli et al., 2016; Peate et al., 2018) both at T0 and T1. At T0, the pain will be assessed before the possible administration of local anesthetic, while we do not expect differences between the intervention and the control group. Finally, the eventually analgesic use during the previous 4 hours will be recorded both at T0 and T1.

Procedure

An alphanumeric code will identify each patient in the case report form (CRF) and in the electronic database used for the analyzes, in order to guarantee pseudonymization.

We will report in the CRF the variables described in the Table 2.

Once the fracture reduction maneuver has been performed and the immobilization performed in a plaster cast, if the patient belongs to the intervention group, we will apply the tape only to the fingers of the hand with a lymphatic technique (Figure 2). We will not extend the application to the

metacarpals even if it would increase the surface of action, because portions of the tape will remain under the plaster, hiding possible skin reactions to the glue. Moreover, the tape application up to the metacarpals, inevitably performed before cast application, will increase the risk of detaching during the plaster wrap.

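### Adjusting for the T0 values already collected (ANCOVA) would usually sharpen the circumference and pain comparisons at almost no cost; the gain is in efficiency only

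*Combined protocol and SAP*

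**What the plan says.** The Primary endpoints section defines the thumb endpoint as the "difference in the circumference of the thumb between baseline (T0) and 7-days follow-up (T1") and treats the other four fingers, measured together, in the same way. Under Outcome evaluation details, circumference is taken on the thumb and "at the base of the 1st phalanx of the remaining 4 fingers merged together both at T0 and T1", and the NRS is also recorded at both times. Table 2 confirms this for all three measures.

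The Statistical analysis section then compares arm means of "the T0-T1 differences of circumference of both thumb (*i*) and the other 4 fingers (*ii*), the pain NRS score at T1(*iii" by t-test for independent groups. T0 circumference enters only by subtraction. T0 pain has no stated part in the treatment comparison. Baseline data otherwise serve to describe the groups and to check the randomisation. No ANCOVA, regression or other adjusted comparison is planned. For missing endpoints, "missing data will be substituted by multiple imputation", with no imputation model given.

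**The concern.** A t-test on change assumes that a patient who starts 1 cm larger ends 1 cm larger. A t-test on T1 pain assumes that T0 pain says nothing about T1 pain. ANCOVA estimates that slope from the data for one degree of freedom. In large samples it is never less precise than either fixed choice. If the true slope is away from 1 (circumference) or 0 (pain), the planned tests give wider intervals and less power than the collected data allow, for both primary endpoints and for pain.

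One condition behind any use of T0 is not settled. The Setting section lists "application of the tape for the investigational treatment patient group, and endpoint T0 measurements will take place at the OER service". A list need not be a sequence, but nothing states that T0 circumference is taken before allocation and taping. The Randomization section adds: "The Investigators are not allowed to collect data in a blind way due to the nature of study intervention".

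**Working it through.** **Inputs from the protocol.** Effect size 0.4, alpha 0.05 two-sided, power 0.80, 1:1 allocation; "The resulting sample size is 100 subjects per arm".

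**Inputs assumed.** The documents give neither r, the T0-T1 correlation, nor k = SD(T1)/SD(T0), so a range is shown. The 0.4 is read as SDs of the quantity in the planned t-test.

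**The plan's own figure.** By the noncentral t distribution, a two-sample t-test with d = 0.4 needs 100 per arm and has power 0.804. The stated sample size reproduces.

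**Variance ratios.** The slope of T1 on T0 is b = r·k.

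- Circumference, ANCOVA against change score: k²(1 − r²)/(1 + k² − 2rk).
- Pain, ANCOVA against T1 alone: 1 − r².
- Both are multiplied by 1 + 1/(N − 4) = 197/196 = 1.0051 at N = 200, the price of estimating the slope.

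The change in interval width is √ratio − 1. Power uses d = 0.4/√ratio on 197 degrees of freedom. Example, k = 1 and r = 0.5: 0.75/1 × 1.0051 = 0.754, and √0.754 = 0.868, so the interval is 13.2% narrower and power is 0.900.

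**Circumference (planned test: power 0.804)**

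| k | r | slope | variance ratio | interval width | power |
|---|---|---|---|---|---|
| 0.9 | 0.5 | 0.45 | 0.671 | 18.1% narrower | 0.930 |
| 0.9 | 0.7 | 0.63 | 0.755 | 13.1% narrower | 0.900 |
| 0.9 | 0.9 | 0.81 | 0.814 | 9.8% narrower | 0.877 |
| 1 | 0.5 | 0.50 | 0.754 | 13.2% narrower | 0.900 |
| 1 | 0.7 | 0.70 | 0.854 | 7.6% narrower | 0.861 |
| 1 | 0.9 | 0.90 | 0.955 | 2.3% narrower | 0.821 |
| 1 | 0.95 | 0.95 | 0.980 | 1.0% narrower | 0.812 |
| 1.1 | 0.5 | 0.55 | 0.822 | 9.4% narrower | 0.874 |
| 1.1 | 0.7 | 0.77 | 0.926 | 3.8% narrower | 0.833 |
| 1.1 | 0.9 | 0.99 | 1.0047 | 0.2% wider | 0.802 |
| 1.25 | 0.5 | 0.625 | 0.897 | 5.3% narrower | 0.844 |
| 1.25 | 0.7 | 0.875 | 0.986 | 0.7% narrower | 0.809 |
| 1.25 | 0.8 | 1.00 | 1.0051 | 0.25% wider | 0.802 |

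**Pain, against T1 alone.** The ratios at r = 0, 0.1, 0.3 and 0.5 are 1.0051, 0.9951, 0.915 and 0.754. The interval is 0.25% wider, then 0.2%, 4.4% and 13.2% narrower.

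**Break-even.** ANCOVA gains once the squared correlation of T0 with the analysed quantity exceeds 1/197, that is |correlation| above 0.071. For pain this is |r| = 0.071. For circumference the no-gain slopes are about 0.990 to 1 at k = 1, 0.962 to 1.028 at k = 1.1, and 0.941 to 1.049 at k = 1.25. At k = 1 this follows from (1 − r)/2 = 1/197, so r = 1 − 2/197 = 0.990.

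**Simulation check.** In 10,000 trials for each of six (k, r) pairs, type I error was 4.8-5.3% for the change score and 4.5-5.4% for ANCOVA (Monte Carlo SE 0.2 points). Simulated power, change score then ANCOVA, was 0.805 and 0.896 at k = 1, r = 0.5; 0.799 and 0.817 at k = 1, r = 0.9; 0.808 and 0.805 at k = 1.25, r = 0.8. These agree with the formulas.

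**T0 timing.** If arm shifted T0 by d0 and left T1 unaffected, the change score would be biased by d0 in size and ANCOVA by slope × d0. Both need T0 to be unaffected by arm.

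**The case against.** Nothing in the plan is wrong here. The endpoint is a change, the test compares that change, and the sample size reproduces for that test. The same fingers measured at the same site seven days apart should correlate highly, and there the gain can vanish. At k = 1.1 the interval is about 0.4% narrower at r = 0.85, 0.2% wider at 0.9 and 0.6% narrower at 0.95. The no-gain band, narrow as a slope, is wider as a correlation: dividing by k gives about 0.875 to 0.935 at k = 1.1 and 0.753 to 0.839 at k = 1.25. Pain may correlate weakly, since "At T0, the pain will be assessed before the possible administration of local anesthetic" and T1 is day 7 in a cast. T0 timing and the imputation model are separate matters that do not favour ANCOVA.

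Most of this stands. The planned tests are valid under the stated condition, the size of the gain is unknown, and T0 timing bears on both methods equally. It does not remove the case for adjusting. A high correlation makes the circumference gain small only when the SDs are similar or T1 is moderately more variable. For k below 1 the ratio is largest at r = k, where it equals k² before the small-sample factor, so at k = 0.9 the interval is at least 9.8% narrower whatever r is. The trade is also one-sided: a possible gain of several points of power against a loss of at most 0.804 − 0.802 = 0.002.

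**Conclusion.** The concern holds as an efficiency point. No planned between-arm analysis uses T0 as a covariate, and at about 200 analysed patients adjustment is more precise outside a narrow set of slopes near 1 (circumference) or correlations near 0 (pain). With r from 0.5 to 0.95 and k from 0.9 to 1.25, the tabulated circumference results run from 18.1% narrower to 0.25% wider. If r is high and k is 1 or slightly above, expect roughly 0 to 2%. For pain, r from 0 to 0.5 gives 0.25% wider to 13.2% narrower. All of this rests on assumed r and k, 100 analysed per arm, and T0 unaffected by arm. The change is recommended; the plan's validity does not depend on it.

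**What to change.** In the Statistical analysis section, before any analysis by arm:

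- For each circumference, make the main analysis a linear model of the T1 value on arm plus the T0 value, reporting the adjusted mean difference with its 95% CI. Modelling the change on arm plus T0 gives the same arm effect apart from sign, so the stated endpoint is kept.
- Analyse T1 NRS on arm plus T0 NRS.
- Keep the planned t-tests as supportive analyses.
- Include arm and the T0 value in the multiple-imputation model.
- State that T0 circumference is measured before allocation and taping.

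The cost is this wording and one degree of freedom per model, with no new data, visits or patients. If T0 circumference is at present taken after allocation or taping, the order of measurement would have to change, which the planned change score needs just as much.

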PROTOCOL

Official title: Randomized and Controlled Prospective Study on Use of the Adhesive Elastic Tape to Control Hand Edema in Patients With a Wrist Fracture Treated With Forearm Plaster

NCT number NCT04683887

Document version 2.0

Document date 15 feb 2022

INTRODUCTION

Wrist fractures are a very common event affecting patients of all ages (Crowe et al., 2020) and are estimated to represent approximately 10-25% of all fractures (Geraci et al., 2011; Smeraglia et al., 2016; Watson et al., 2018). These fractures are treated with closed reduction and forearm circular cast in 70-90% of cases (Letsch et al., 2003). There are several immobilization techniques, although there is no evidence identifying the best one in maintaining reduction. The forearm circular cast seems to be the best tolerated by patients (Okamura et al., 2018; Park et al., 2017; Peivandi et al., 2011).

Wrist fracture patients often develop oedema (Knygsand-Roenhoej & Maribo, 2011) and the presence of plaster increases the risk (Dresing et al., 2017). In 2019, 17.4% of patients with wrist fractures treated with circular plaster cast at one Orthopedic Emergency Room (OER) of Northern Italy, had a second visit in OER for oedema, pain or "intolerance to the plaster cast".

Kase has developed an adhesive elastic tape from 1973 to 1979 and marketed in 1982 with the name Kinesio tape (Wu et al., 2015). Since then, several authors have described this technique (Kase, 2005; Blow, 2015; Kumbrink et al., 2019) and several companies have started producing tapes with analogue characteristics. These devices are thin elastic stripes usually made of cotton, containing longitudinal interwoven elastic fibers and acrylic glue that is spread in a wavelike pattern. The material elasticity is approximately 130–140%, and the amount of traction used in its application to the skin influences the skin itself and various subcutaneous layers (Kase, 2005; Blow, 2015; Kumbrink et al., 2019). Taping technique is used to control the oedema, support of soft tissues, protect the joints and alleviate the heat produced by active inflammation.

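### Secondary endpoint (iii) counts re-entries for cast intolerance, but the CRF as listed records no reason for re-attendance, so the endpoint cannot be derived from it; a minor second point is a normality check on the outcome t-tests with no alternative named

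*Combined protocol and SAP*

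**What the plan says.** **Endpoint.** Methods, Secondary endpoints, defines item (iii) as "OER re-entry number for “intolerance to the plaster cast". The Introduction reports that in 2019, at one OER, 17.4% of patients with a circular cast "had a second visit in OER for oedema, pain or" cast intolerance, so the sponsor itself names three reasons.

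**Collection.** Outcome evaluation details: "The number of re-entries in OER between T0 and T1 will be registered". Procedure: "CRFs will be kept in OER until follow-up, so that any re-attendances can be noted". Procedure also says that the CRF carries the variables of Table 2. Table 2 has one re-attendance line, a natural number entered at T1, and no line for the reason. Under Follow up, the completed CRFs are what the analysing researcher receives.

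**Analysis.** The Statistical analysis section compares "the number of OER re-entries (*v*), by t-test for independent groups (after verifying the normality of the distributions with the Shapiro Wilk test". The same sentence covers "the T0-T1 differences of circumference of both thumb (*i*) and the other 4 fingers (*ii" and NRS at T1. No other method is named for these four outcomes. The baseline t-test stands in an earlier sentence and carries no normality condition.

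**Related text.** Statistical analysis anticipates tape loss ("In the event of tape detachment in the first 48 hours after T0"), and Table 2 has two accidental-removal lines. On blinding, Randomization, blind and control says "The data-analyzing Researcher will not know which of the two groups will be the intervention nor the control one"; the staff who collect the data are not blinded.

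**The concern.** Cast tolerability is a stated aim, and endpoint (iii) is its only direct measure. If the plan is followed as written, the analyst receives a count of all re-attendances and cannot separate those due to cast intolerance. The quantity tested then differs from the quantity declared. Some reasons for returning, such as a detached tape or a skin reaction to it, can arise only in the tape arm and would count against the tape although they say nothing about the cast.

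The second matter is smaller. The outcome t-tests follow a Shapiro-Wilk check, and the plan does not say what happens if the check fails. A test would then be chosen after the data are seen, possibly for the primary endpoints too. Blinding the analyst to group identity limits this without removing it: coded groups hide the direction of a difference but not its p-value.

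**Working it through.** **1. Can endpoint (iii) be derived?**

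| Place | What is counted | Reason attached? |
|---|---|---|
| Secondary endpoints | re-entries | yes, cast intolerance |
| Introduction (2019 figure) | second visits | yes, three reasons pooled |
| Outcome evaluation details | re-entries, T0 to T1 | no |
| Procedure | any re-attendance | no |
| Table 2 | one natural number | no |
| Statistical analysis | re-entries | no |

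No CRF line supplies the qualifier in the first row. The accidental-removal lines show that a tape came off, not whether a visit followed, so tape-related visits cannot be subtracted either. The size of the resulting distortion cannot be computed from the documents.

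**2. The plan's sample size.** Inputs from Sample size calculation: effect size 0.4, alpha 0.05 (two-sided), power 0.80. The normal formula gives n = 2(1.960 + 0.842)² / 0.4² = 98.1, so 99 per arm. The exact t-test calculation gives 99.08, so 100 per arm, as stated. Neither matter changes this.

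**3. Would the Shapiro-Wilk check be passed?** Simulation with 100 per arm, check run per arm at 0.05. The documents give no SD, reading precision or 7-day rate, so every distribution here is an assumption.

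- Re-entry count, Poisson means 0.02 to 0.30: every non-constant sample is rejected. For 0/1 data, the largest p-value over all 99 possible splits of 100 is 2.2 × 10⁻¹⁴.
- Integer NRS, mean 2 to 5, SD 1.5 to 2.5: 92% to 100% rejected.
- Circumference change, normal, T0 and T1 readings each rounded (at least one of two arms = 1 − (1 − p)²):

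| SD (cm) | 0.1 cm readings, per arm | 0.5 cm readings, per arm |
|---|---|---|
| 0.3 | 0.266 | 1.00 |
| 0.5 | 0.090 | 1.00 |
| 0.7 | 0.072 | 1.00 |
| 1.0 | 0.060 | 0.894 |

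At SD 0.3 and 0.1 cm, 1 − 0.734² = 0.461; at SD 1.0 and 0.5 cm, 1 − 0.106² = 0.989. Exactly normal, unrounded data fail in at least one arm with probability 1 − 0.95² = 0.0975.

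**4. Does a failed check do harm?** Type I error of the t-test itself: 0.040 to 0.050 for counts, 0.048 to 0.051 for NRS, 0.050 to 0.053 for rounded circumference. Always reporting the smaller of the t-test and Mann-Whitney p-values: 0.049 and 0.061 for counts (means 0.05 and 0.174), 0.058 for NRS, 0.057 for circumference (0.5 cm readings, SD 0.5), 0.067 for a skewed change (gamma, shape 2).

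**5. What a cause-specific count costs in power.** Illustration: 100 per arm, 0/1 outcome, assumed control rate p halved by tape. Approximate power = Φ(d/SE − 1.96), with d = p/2 and SE = √{[p(1 − p) + (p/2)(1 − p/2)]/100}.

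| p | d | SE | Approximate | Exact enumeration, t-test |
|---|---|---|---|---|
| 17.4% | 0.087 | 0.0472 | 45% | 45.5% |
| 10% | 0.050 | 0.0371 | 27% | 27.0% |
| 5% | 0.025 | 0.0268 | 15% | 13.2% |

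The 17.4% is the Introduction's pooled figure, not a rate for endpoint (iii).

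**The case against.** **On the endpoint.** The 2019 figure shows that reasons for a second visit have been retrievable at an OER, and the CRFs stay where patients would return, so the information may be recoverable. That stands, and it limits the claim to the CRF as listed. It does not close the gap: no section provides for extracting the reason or defines intolerance. A reader might infer that the documents declare an all-cause endpoint, or that the comparison is materially biased against the tape. Neither is supported. The unqualified wording is an omission, and tape-related visits are of unknown number, probably few given Table 1's skin and allergy exclusions.

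**On the t-test.** The text can be read as naming the t-test and attaching a diagnostic, since nothing says that the t-test is dropped if the check fails. The usual path (t-test if both arms pass, otherwise Mann-Whitney) also had type I error of 0.042 to 0.053 in simulation. Both arguments stand, and they make this a matter of clarification. A reader might infer that the t-test is invalid, that the primary analysis is compromised, or that every t-test in the section is affected. The figures do not support the first. The second rests on a reading precision that the documents do not give. The third is wrong, because the baseline t-test has no such condition.

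**Conclusion.** The main point holds and should be acted on: endpoint (iii) as declared cannot be derived from the CRF as listed, and following the plan yields a different quantity. This rests on the text alone and needs no assumed figure, but its numerical effect cannot be estimated.

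The second point holds as a minor one, for the four between-group outcomes only. The re-entry count cannot meet the written condition and NRS very probably will not. Whether the circumference changes do is open: under the assumed SDs of 0.3 to 1.0 cm, at least one of two arms fails in 12% to 46% of trials with 0.1 cm readings and in 99% to 100% with 0.5 cm readings. The consequence is an unspecified path, with type I error of about 0.05 to 0.07 at worst in the assumed scenarios.

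**What to change.** **Endpoint.** Add to Table 2's re-attendance line a coded reason for each visit: cast intolerance, oedema, pain, tape or skin problem, other. Because these overlap, add a written definition of cast intolerance and a rule for visits with several reasons, for example tick all that apply and count the visit for endpoint (iii) if intolerance is ticked. Analyse endpoint (iii) as Secondary endpoints defines it, and report all-cause re-attendance alongside, because the coders can see the tape. Make Secondary endpoints, Outcome evaluation details, Procedure, Statistical analysis and Table 2 agree.

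The cost is one CRF field at a visit already logged. The drawbacks are partly subjective, unblinded coding and fewer cause-specific than all-cause events, hence the low power illustrated above. Redefining endpoint (iii) as all-cause would avoid the coding but would no longer isolate cast tolerability.

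**Normality condition.** Delete the Shapiro-Wilk condition for both circumference changes, NRS at T1 and re-entries. Keep the independent-groups t-test as the pre-specified test whatever the distribution looks like, and report each mean difference with its 95% CI. Naming a fallback, or a count or binary method for re-entries, would also close the gap; keeping the t-test is the smallest edit, and its type I error in the scenarios checked supports it. The cost is one deleted clause, with the sample size unchanged.
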